7.2 Packaging and Labeling

7.2.1 Packaging

One DCS of the IP is contained in a small box.

7.2.2 Labeling

The small box is labeled with a statement for clinical study use only, the name and address of the sponsor, identification number, lot number, and storage method.

7.3 Storage and Management of Investigational Products

The investigational product manager at each study site will store and manage the IPs according to the “Operating Procedure for Investigational Product Management” prepared by the sponsor and other procedures specified at each site.

8. Treatment Method

8.1 Dispensing of Investigational Products

The investigator or subinvestigator will dispense one DCS of the IP at the following visits:

<Dispensing visits>

Day of study treatment initiation, Week 4, 8, 12, 16, 20, 24, 28, 32, 36, 40, 44, and 48

8.2 Preparation of Investigational Products

The investigator or subinvestigator, the investigational product manager or the person in charge of preparation of the IP will prepare injection solutions of IPs according to the “Standard Operating Procedure for Investigational Product Management.”

8.3 Method of Administration

On the days of administration (see Table 9-1: Schedule), the investigator or subinvestigator will subcutaneously inject one DCS (0.6-mL) of nemolizumab slowly to the participant either in the upper arm, abdomen, or thigh. The IP may be administered by a person qualified to administer it under the instruction of the investigator or subinvestigator.

- Precautions

- The IP will be administered after all observation/tests scheduled at the visit have been completed.
- The IP will be administered within the window of the specified visit. However, if the IP cannot be administered within the window, the next dose should be administered 14 days or later after the

previous dose.

- If the participant's body weight is lower than 30.0 kg on the day of administration, the IP must not be administered.

- Rationale for selection>

- 1) Dosage: 60 mg/body Q4W

A phase III study in Japanese patients with atopic dermatitis has demonstrated the long-term safety of nemolizumab 60 mg/body Q4W. This study has been designed to exploratorily evaluate the efficacy of nemolizumab in SSc patients at 60 mg/body Q4W which has shown the long-term efficacy in SSc patients.

- 2) Treatment Period

The treatment period has been set at 52 weeks because long-term observation is required to evaluate the efficacy of nemolizumab on skin thickening in SSc patients in an exploratory manner.

- 3) Day of Follow-up Visit

Considering the serum elimination half-life after a single dose of nemolizumab ranges from 12.6 to 14.6 days in patients with atopic dermatitis, the day of follow-up visit has been set to collect information such as the occurrence of adverse events on the day of 5 times the elimination half-life (84 days \pm 7 days) from the day of the last dose.

8.4 Concomitant Medications and Therapies

8.4.1 Restricted Concomitant Medications

The following medications may be continued at a stable dose if used for at least 14 days before the day of study treatment initiation. However, the dose may be reduced at the discretion of the investigator or subinvestigator, and after dose reduction, the dose may be increased up to that used at the day of study treatment initiation.

- Oral steroids (\leq 10 mg/day of prednisolone or equivalent)

8.4.2 Duration and Method of Inspection

The investigator or subinvestigator will collect the information of concomitant medications/therapies by interviewing participants according to Section [9.3.2](#)

8.4.3 Prohibited Concomitant Medications and Therapies

Concomitant use of medications and therapies listed below is prohibited in this study.

- From the day of study treatment initiation to Week 52 or to the physical examination on the day of visit for discontinuation
- 1) The following systemic medications:
 - a) Antifibrotic drugs (e.g., pirfenidone, nintedanib)
 - b) Immunosuppressants (e.g., cyclophosphamide, cyclosporine, tacrolimus, azathioprine, mycophenolate mofetil, mizoribine, sulfasalazine, leflunomide, methotrexate, hydroxychloroquine, D-penicillamine, sirolimus)
 - c) Tyrosine kinase inhibitors (e.g., imatinib)
 - d) JAK inhibitors (e.g., tofacitinib, upadacitinib)
 - e) Endothelin receptor agonists (e.g., bosentan, ambrisentan, macitentan)
 - f) Phosphodiesterase-5 inhibitors (e.g., sildenafil, tadalafil)

- g) Prostaglandin analogues (e.g., alprostadil, epoprostenol)
- h) Riociguat
- 2) Injections of corticosteroids (excluding joint injections)
- 3) Phototherapy
- 4) High-dose intravenous immunoglobulin therapy
- 5) Antibody drugs
- 6) Live vaccines

- Rationale for selection

1) 2) 4) 5)	Established considering the impact on the efficacy of the IP and the safety of participants
3)	Established considering the impact on the efficacy evaluation of the IP
6)	Established considering the safety of participants

- From the day of study treatment initiation to the day of follow-up visit
 - 1) Other drugs and medical devices under development

- Rationale for selection

1)	Established considering the safety of participants and the impact on the efficacy of the IP.
----	--

8.4.4 Instructions to participants

The investigator or subinvestigator will examine the implementation status of the treatment of SSc at each visit and give instructions to the participants on treatment of SSc according to the therapeutic guidance specified in Sections [8.4.1](#) and [8.4.3](#).

9. Study Procedures and Assessments and the Schedule

9.1 Schedule of Study Procedures and Assessments

Observation, tests and sample collection will be performed according to the schedule shown in [Table 9-1](#).

Table 9-1: Schedule

Visit	1		2	3	4	5	6	7	8	9	10	11	12	13	14	15	16	17/ discont	FU
Visit name	IC day	Screening	Treatment initiation	W 1	W 2	W 4	W 8	W 12	W 16	W 20	W 24	W 28	W 32	W 36	W 40	W 44	W 48	W 52 or discont	FU ^U
Reference day	-	-14	1	8	15	29	57	85	113	141	169	197	225	253	281	309	337	365/ discont	Day of last dose +84
Visit window	-	- 16/+9	-	±2	±3	±3	±3	±3	±3	±7	±7	±7	±7	±7	±7	±7	±7	±7/ day of discont+14	±7
Screening/management																			
Informed consent	X ^a																		
Physical examinations	X	X	X	X	X	X	X	X	X	X	X	X	X	X	X	X	X	X	X
Demographics	X	X	X																
Body weight		X	X			X	X	X	X	X	X	X	X	X	X	X	X		
Registration		X 1 st	X 2 nd															X Time of discont	
Efficacy evaluation																			
mRSS ^b		X	X			X		X			X			X				X	X
Respiratory function test ^c		X						X			X							X	
Chest HRCT ^d		X									X							X	

Visit	1		2	3	4	5	6	7	8	9	10	11	12	13	14	15	16	17/ discont	FU
Visit name	IC day	Screening	Treatment initiation	W 1	W 2	W 4	W 8	W 12	W 16	W 20	W 24	W 28	W 32	W 36	W 40	W 44	W 48	W 52 or discont	FU ^j
Severity classification of the lung		X									X							X	
ACR-CRIS								X			X							X	
Number of digital ulcers		X	X					X			X			X				X	
Physician's Global Assessment			X					X			X			X				X	
HAQ-DI			X					X			X			X				X	
FACIT-Fatigue			X					X			X			X				X	
FSSG			X					X			X			X				X	
Patient's Global Assessment			X					X			X			X				X	
Safety evaluation																			
Vital signs		X	X	X		X	X	X	X	X	X	X	X	X	X	X	X	X	X
Echocardiography		X									X							X	
Electrocardiogram		X									X							X	
Photography ^e			X																
Laboratory tests																			
Hematology Blood chemistry TARC Urinalysis		X	X	X		X	X	X	X	X	X	X	X	X	X	X	X	X	X
Pregnancy ^f and TB ^g tests		X																	
Hepatitis B and C tests ^h		X						(X)			(X)			(X)			(X)		(X)
Antinuclear antibodies test			X																

Visit	1		2	3	4	5	6	7	8	9	10	11	12	13	14	15	16	17/ discont	FU
Visit name	IC day	Screening	Treatment initiation	W 1	W 2	W 4	W 8	W 12	W 16	W 20	W 24	W 28	W 32	W 36	W 40	W 44	W 48	W 52 or discont	FU ¹
PK analysis and immunogenicity																			
Serum nemolizumab concentrations			X	X	X	X	X	X	X	X	X			X				X	X
Anti-nemolizumab antibody assay			X								X			X				X	X
Biomarkers																			
IL-31			X			X	X	X	X	X	X			X				X	
KL-6, SP-D, NT-proBNP			X			X		X			X			X				X	
Exploratory biomarkers			X					X			X							X	
Investigational product administration																			
Administration ⁱ			X			X	X	X	X	X	X	X	X	X	X	X	X		
Others																			
Comprehensive measurement of autoantibodies			X								X							X	
CyTOF measurement			X								X							X	
Adverse Events																			
Concomitant medications and therapies																			

^a To be obtained before the observation/tests for the study, and may be obtained on the same day as the day of screening

^b In principle, the same investigator or subinvestigator will evaluate each participant throughout the study.

^c If the %FVC decreases by $\geq 15\%$ from baseline, %FVC will be measured again within 1 month.

^d If having been performed within 1 month of the specified timepoint, not necessary to be performed at the specified timepoint, and the results within 1 month will be substituted.

^e Not to be performed if refused by the participant.

If any of the following treatment-emergent adverse events occurs, photographs of the affected skin areas of the adverse event should be taken while the event (at least once) is occurring and at the final outcome evaluation, in addition to the scheduled visit (i.e., the day of study treatment initiation). The photography on the scheduled visit (day of study treatment initiation) will be performed according to Section 9.3.5.4

- Atopic dermatitis
- Adverse events with skin symptoms of edematous erythema or scaling
- Any other adverse event for which the investigator or subinvestigator considers that photography is necessary.

^f To be performed on female participants excluding those who never become pregnant.

^g May be conducted on another day after the day of screening before the day of study treatment initiation

^h • Hepatitis B

The participants who test negative for HBs antigen and positive for HBc antibody will undergo HBV-DNA measurement before the day of study treatment initiation. The participants enrolled through HBV-DNA measurement will undergo HBV-DNA measurement once every three months.

• Hepatitis C

The participants who test positive for anti-HCV antibody will undergo HCV-RNA measurement before the day of study treatment initiation. The participants enrolled through HCV-RNA measurement will undergo HCV-RNA measurement once every three months.

ⁱ To be administered after all observation/tests are performed. If the IP cannot be administered within the window indicated, the next dose should be administered 14 days or later after the day of the previous dose.

^j Participants who discontinued the study will visit the site 84 days (± 7 days) after the day of the last dose of study treatment for observation/tests at FU shown in [Table 4-1](#). Participants discontinued the study before study treatment initiation need not to undergo observation/tests scheduled on the day of visit for discontinuation.

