2.2 Secondary Objective

To evaluate the safety and pharmacokinetics of nemolizumab in SSc patients with moderate to severe skin thickening

3. Study Design

This is a phase II, single-arm, multiple-dose study consisting of a pre-treatment observation period (1-4 weeks) and a treatment period (52 weeks). The pre-treatment observation period is from the day of screening to the day of study treatment initiation, and participants will visit the site a total of twice, for screening and for study treatment initiation. The treatment period is from the day of study treatment initiation to Visit 17 (Week 52), during which participants will visit a total of 15 times: Week 1, 2 and 4, and every four weeks thereafter. Participants having received study treatment will be followed up 84 days after the day of the last dose of study treatment. Follow-up period is from Visit 17 (Week 52) or the day of discontinuation visit to the day of follow-up visit.

[figure not shown]
Study phase: Phase II

Study type: Open-label, single-arm, multiple-dose study

Participants: SSc patients with moderate to severe skin thickening

Target Sample Size: 8 participants

Figure 3-1: Study Schema

1) Pre-treatment observation period

The investigator or subinvestigator will make observations and assessments at the screening visit specified in [Table 9-1](#) after obtaining informed consent from the participant.

2) Treatment period

The investigator or subinvestigator will administer the investigational product (IP) (nemolizumab, 60 mg/body) every 4 weeks (Q4W) at visits until Week 48 after making observations and assessments on the day of study treatment initiation specified in [Table 9-1](#). In addition, the investigator or subinvestigator will make perform observations and assessments at each visit specified in [Table 9-1](#).

3) Follow-up period

All participants having received the IP will be scheduled to visit for follow-up 12 weeks after the day of the last dose of study treatment (the day of follow-up visit). On the day of the follow-up visit, the investigator or subinvestigator will evaluate the safety and efficacy after completion of study treatment for all participants.

4. Target Indication and Inclusion and Exclusion Criteria for Participants

The investigator or subinvestigator will ensure before enrollment that all inclusion criteria are met and none of the exclusion criteria are met.

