8) Patients whose laboratory test values on the day of screening meet any of the following criteria: a) AST or ALT > 2 times the upper limit of normal b) Serum creatinine ≥2.0 mg/dL c) WBC <3000 cells/μL	—	—	X
9) Patients infected with hepatitis B virus (HBV) or hepatitis C virus (HCV) (Positive for HBs antigen or HBc antibody on the day of screening, positive for anti-HCV antibody on the day of screening) The allowed exceptions are as follows: • Patients confirmed not to be infected with HBs at the time of the HBV-DNA test performed before study treatment initiation in the case of negative for HBs antigen and positive for HBc antibody in the hepatitis B test	—	—	X

Exclusion Criteria	Confirmation timing		
	Day of informed consent	Day of Screening	Day of treatment start

 performed on the day of screening. Patients confirmed not to be infected with HCV at the time of the HCV-RNA test performed before study treatment initiation in the case of positive for anti-HCV antibody in the hepatitis C test performed on the day of screening 			
10) Patients with latent or active tuberculosis based on the result of the screening TB test. The allowed exception is patients deemed not to be infected with tuberculosis according to the “Guidelines for the use of interferon-γ release assay (Prevention Committee of the Japanese Society for Tuberculosis).	—	—	X
11) Patients with either of the following infectious diseases: 
 Recurrent/chronic infections or other active infections deemed by the investigator to possibly aggravated by participating in the study Infections (including skin infections) requiring systemic antibiotics, antivirals, or antifungals within 7 days prior to the day of study treatment initiation. 	X	X	X
12) Patients who have received oral steroids (> 10 mg/day of prednisolone or equivalent), dosage of receiving oral steroids have been changed (from ≤ 10 mg/day of prednisolone or equivalent), or newly treated with oral steroids, within 14 days before the day of study treatment initiation	—	—	X
13) Patients who have received any of the following therapies within the indicated period prior to the day of study treatment initiation	—	(X)*	X
a) Within 365 days			
Cyclophosphamide			
b) Within 120 days or 5 times the elimination half-life of the drug, whichever is longer			
Antibody drugs			
c) Within 28 days			

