i. Live vaccines ii. The following systemic medications: 
 Antifibrotic drugs (e.g., pirfenidone, nintedanib) Immunosuppressants (e.g., cyclosporine, tacrolimus, azathioprine, mycophenolate mofetil, mizoribine, sulfasalazine, leflunomide, methotrexate, hydroxychloroquine, D-penicillamine, sirolimus) Tyrosine kinase inhibitors (e.g., imatinib) 			

Exclusion Criteria		Confirmation timing		
		Day of informed consent	Day of Screening	Day of treatment start
	
 – JAK inhibitors (e.g., tofacitinib, upadacitinib) – Endothelin receptor agonists (e.g., bosentan, ambrisentan, macitentan) – Phosphodiesterase-5 inhibitors (e.g., sildenafil, tadalafil) – Prostaglandin analogue (e.g., alprostadil, epoprostenol) – Riociguat iii. Injections of corticosteroids (excluding joint injections) iv. Phototherapy v. High-dose intravenous immunoglobulin therapy 			
14)	Patients who are within 120 days from the end of participation in other clinical trials or post-marketing clinical studies (i.e., the last day of administration of another IP or post-marketing clinical study drug) until the day of study treatment initiation, or participating in other clinical trials or post-marketing clinical studies	–	(X)*	X
15)	Women who are pregnant, breastfeeding, possibly pregnant, or unwilling to use appropriate contraception measures as instructed by the investigator during the study period	X	X	X
16)	Patients who meet any of the following criteria: 
 a) Having not met eligibility for participation when participating in this study in the past b) Having previously received nemolizumab (including placebo) 	X	X	X
17)	Patients with confirmed or suspected COVID-19	–	X	X
18)	Patients with a history of confirmed or suspected COVID-19 excluding those meeting any of the following criteria: 
 • At least 20 days after the onset of symptoms and at least 72 hours after the resolution of symptoms. • Confirmed not to carry SARS-Cov-2. 	–	X	X
19)	Patients found to have close contacts with COVID-19 patients within 14 days before the day of study treatment initiation	–	–	X
20)	Other patients who are considered ineligible for the study by the investigator	X	X	X

*The exclusion criteria will be assessed with the expected date of study treatment initiation as the starting point.

• Rationale for exclusion criteria

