9.2.3 Day of Study Treatment Initiation

The day of study treatment initiation is defined as the day when the participant is enrolled after completion of protocol-specified assessments. All assessments scheduled for the day of study treatment initiation must be performed on the same day.

The day of study treatment initiation is Day 1, and the day before the day of study treatment initiation is Day -1.

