9.3.6 Laboratory tests

Laboratory tests will be performed at the central laboratory. The investigator or subinvestigator will collect blood and urine samples from participants before study treatment initiation and submit them to the central laboratory. Tuberculosis test may be performed in an in-hospital laboratory.

- Hematology and serum chemistry tests
- Immunological tests (thymus and activation-regulated chemokines [TARC])
- Urinalysis

Time points	Day of screening, Day of study treatment initiation, Week 1, 4, 8, 12, 16, 20, 24, 28, 32, 36, 40, 44 and 48, Week 52 or Day of discontinuation visit, Day of follow-up visit
Notes	
 1) 2) and 3): 
 On the day of study treatment, blood and urine will be collected before the treatment. The test result should be reviewed before the next study treatment. 1) and 2): 
 When aggregation or coagulation is observed in "Plt" because of a reason other than manual technique, blood will be collected into a blood collecting tube containing 3.2% sodium citrate in addition to a conventional blood collection tube from the next visit.

4) Pregnancy test

Time points	Day of screening
Notes	
 The test will be performed on female participants. However, those who are considered unable to become pregnant (e.g., menopausal women* and women who have had total hysterectomy) will be excluded. *: Defined as those who are amenorrhea for at least 12 months without any medical reason.

5) Tuberculosis test

Time points	Day of screening
Notes	
 If the test cannot be performed on the day of screening, it may be performed on another day after the day of screening but before study treatment initiation. In such cases, the rest results should be reviewed before administration of IP on the day of study treatment initiation.

6) Hepatitis B and C tests

Time points	a) Day of screening b) Week 12, 24, 36 and 48, Day of follow-up visit

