Notes	a) The participants who test negative for HBs antigen and positive for HBc antibody on the day of screening will undergo HBV-DNA measurement before the day of study treatment initiation. The participants who test positive for anti-HCV antibody on the day of screening will undergo HCV-RNA measurement before the day of study treatment initiation. b) The participants enrolled through HBV-DNA measurement before the day of study treatment initiation will undergo HBV-DNA measurement once every three months. The participants enrolled through HCV-RNA measurement before the day of study treatment initiation will undergo HCV-RNA measurement once every three months.

7) Antinuclear antibodies test

Time points	Day of study treatment initiation
Notes	
 Blood will be collected before administration of IP on the day of study treatment initiation

Table 9-2: Clinical Laboratory Assessments

Laboratory tests	Parameters
Hematology	Hb, Ht, Plt, RBC, WBC, differential leukocyte count, MCV, MCH, and MCHC
Serum chemistry	Na, K, Cl, UN, CREA, Ca, T-Bil, D-Bil, TP, ALB, ALT (GPT), AST (GOT) , ALP, P, LDH, CK, UA, TC, LDL-C, HDL-C, TG, A/G ratios, γ -GTs, and CRP
Immunology	TARC
Urinalysis	Protein, occult blood, urinary sugar, and urobilinogen
Pregnancy	Urine hCG
Tuberculosis	Interferon gamma release assay (Central measurement: T-SPOT, in-house examination: T-SPOT or QFT-3G)
Hepatitis B and C	HBs antigen, HBc antibody, HBV-DNA, Anti-HCV antibody, and HCV-RNA
Antinuclear antibodies	Anti-Scl-70 antibodies, anti-centromere antibodies, and anti-RNA polymerase-III antibodies

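### Urine hCG is scheduled only at screening, 5 to 30 days before the first dose, with no test on Day 1, when the pregnancy exclusion must be confirmed again

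*Combined protocol and SAP*

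**What the plan says.** - **Schedule.** In Table 9-1 (Section 9.1) and synopsis Table 4-1, the row "Pregnancy ^f and TB ^g tests" has one mark, under Screening. There is none under Treatment initiation or any later visit. The other two protocol versions in the file also mark this row at Screening only.
- **Section 9.3.6 4).** "The test will be performed on female participants", apart from those considered unable to become pregnant. The only time point is the day of screening. Table 9-2 names the test as urine hCG.
- **Footnotes to Table 9-1.** Footnote f limits who is tested. Footnote g ("May be conducted on another day after the day of screening before the day of study treatment initiation") is attached to the TB test only. Section 9.2.2 requires all other screening tests to be done on the screening day itself.
- **Day 1 urinalysis.** The repeated panel in Table 9-2 is "Protein, occult blood, urinary sugar, and urobilinogen". It contains no hCG.
- **Exclusion 15 (Section 4.3).** "Women who are pregnant, breastfeeding, possibly pregnant, or unwilling to use appropriate contraception measures as instructed by the investigator during the study period". It is marked for confirmation at informed consent, at screening and on the day of treatment start. The rationale table gives participant safety as the reason.
- **Exclusion 8 (Section 4.3).** This is also checked on the day of treatment start, but it names its basis: "Patients whose laboratory test values on the day of screening meet any of the following criteria".

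**The concern.** Exclusion 15 asks about a state that can change between screening and Day 1. The plan requires the investigator to judge it again on Day 1 but schedules no Day 1 test to support that judgement. Exclusion 8 shows that the protocol says so when a Day 1 check is meant to rest on screening values; exclusion 15 carries no such statement.

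At stake is a first dose given in an unrecognised early pregnancy that a same-day test might have found. Sections 5.1 5) and 11.8 require treatment to stop, but only once a pregnancy is known. Stopping later doses does not withdraw the first. With the half-life of 12.6 to 14.6 days in Section 8.3 (measured in atopic dermatitis), five half-lives are 5 × 12.6 = 63 to 5 × 14.6 = 73 days.

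**Working it through.** The plan gives no figure of its own for this interval, so there is none to reproduce. The check is day arithmetic plus a reading of every place where a test could be scheduled.

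**Inputs**
- Screening reference day −14, window −16/+9 (Table 9-1).
- Day numbering: "The day of study treatment initiation is Day 1, and the day before the day of study treatment initiation is Day -1" (Section 9.2.3). There is no Day 0, so Day −k is k days before the first dose.
- Pre-treatment period of 1 to 4 weeks (Section 3).
- Week 4 dose on Day 29 ± 3 (Table 9-1).
- Target of 8 participants (Section 17.4.1).

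**Gap from the only test to the first dose**
- Earliest screening: −14 − 16 = Day −30, or 30 days before.
- Latest screening: −14 + 9 = Day −5, or 5 days before.
- Nominal: Day −14, or 14 days before.
- By the Section 3 text: 1 × 7 = 7 to 4 × 7 = 28 days. The window and the text differ slightly; on either reading the gap is roughly 1 to 4 weeks.

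**Scheduled hCG tests.** One at screening, none on Day 1, none later. Footnote g does not move the test, and the Day 1 urinalysis does not include it.

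**Would a Day 1 sample sent to the central laboratory be enough?** Section 9.3.6 sends laboratory tests to the central laboratory. For the routine panels, items 1) to 3), it asks only that results be reviewed before the next dose. If a Day 1 hCG were handled under that rule, the next dose is at Week 4:
- Nominal: 29 − 1 = 28 days later.
- Window: 26 − 1 = 25 to 32 − 1 = 31 days later.

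Such a result could arrive after the first dose, so a useful Day 1 test has to be read at the site.

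**Added tests.** 1 per non-exempt woman × at most 8 participants = at most 8.

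**The case against.** The strongest reply is that a mark against an exclusion criterion asks the investigator to confirm it and does not by itself call for a laboratory test. Exclusion 15 is also marked at informed consent, where no pregnancy test is scheduled. Exclusion 5 (immune deficiency, including HIV) is marked at all three times, although Table 9-2 lists no HIV test. That is correct, and it is why this is a design weakness and not a contradiction in the protocol.

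The interval also has some protection. Contraception is required throughout the study period, which Section 11.10 runs from informed consent to the follow-up visit. A woman who is only possibly pregnant is already excluded on Day 1. A physical examination is scheduled that day, exclusion 20 gives the investigator discretion, and Section 9.3.14 allows for additional tests. These points stand, but they reduce the risk without closing it: none guarantees a test result before the first dose.

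Two further points are fair. A Day 1 test can also miss a very early pregnancy, and the documents give no assay sensitivity, so the benefit cannot be sized. And if contraception and event-driven action are accepted for the 12 later doses (Week 4 to Week 48), one may ask why they are not enough for the first. The answer is that Day 1 is the only dosing day on which the protocol requires exclusion 15 to be confirmed. Leaving later tests to the sponsor does not remove what is gained on Day 1.

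**Conclusion.** The concern holds, as a change the sponsor should make. With the protocol followed exactly, the first dose can be given 5 to 30 days after the only pregnancy test (7 to 28 days by the Section 3 text), and no test is scheduled on Day 1. No inconsistency is claimed for the later dosing visits, because Sections 5.1 5) and 11.8 act only when a pregnancy is found.

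The conclusion rests on the schedule and the visit window, and confidence in those facts is high. It does not rest on an estimate of harm. The documents leave anticipated reactions to the investigator's brochure (Section 11.12) and do not say how many of the 8 participants could become pregnant, so no probability of pregnancy and no harm rate can be given.

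**What to change.** 1. In Section 9.3.6 4), add the day of study treatment initiation as a second time point for women not exempt under the existing note, with the result read before administration.
2. In Tables 9-1 and 4-1, split the shared pregnancy and TB row and mark the pregnancy test under Treatment initiation, so that no second TB test is created.
3. Amend the central-laboratory sentence in Section 9.3.6 so that the Day 1 hCG may be read at the site, as an in-hospital test is already allowed for tuberculosis.

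Section 8.3 already places scheduled tests before dosing, and urine is already collected before treatment on Day 1. A positive result would be handled under exclusion 15 before second registration. Optionally, tests could be repeated at some or all dosing visits from Week 4 to Week 48, at a frequency the sponsor sets from the investigator's brochure.

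**Cost.** A protocol amendment and one urine kit per non-exempt woman, at most 8 in all, with no extra visit or urine collection. Table 9-3 lists 10 mL of urine at screening, when hCG is scheduled, and 10 mL on Day 1. It does not divide the volume between tests, so the site should confirm that an aliquot can be kept. The downsides are a site reading step of a few minutes and a first dose held while any positive result is confirmed.
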